678 PCOS women actively seeking pregnancy (or 226 per each treatment arm) aged 18-39 years will be enrolled in the 12 sites (eight Reproductive Medicine Network centers and four U54-SCCPRR centers) over a 2-year enrollment period. The overall goal of the inclusion and exclusion criteria is to identify a population of healthy PCOS women with anovulation as the exclusive infertility factor. Local laboratory cutoffs for inclusion/exclusion values may vary according to assay methodology. Where existing medical records are used to verify inclusion or exclusion criteria, the site should keep a copy of these in the source documents. A general list of exclusionary medications requiring a washout period is found in appendix D. This list is not exhaustive and questionable medications can be looked up to see if they belong to one of the families of exclusionary medications or the DCC can be queried.

Inclusion Criteria

1. Chronic oligo/anovulation. Oligomenorrhea defined as spontaneous intermenstrual periods of ≥ 45 days or a total of ≤ 8 menses per year. For women who have been on ovarian suppressive therapy or other confounding medication (i.e. insulin sensitizing agents) within the last year prior to the study, a history of ≤ 8 menses per year prior to the initiation of this prior therapy will qualify as evidence of oligomenorrhea.
2. Hyperandrogenemia defined by either an elevated total testosterone, or free and weakly bound testosterone, or free testosterone as determined by normative values at each local lab in the multicenter study. Any or all of these measures of circulating testosterone levels can be obtained, although an elevated level of any one of them is sufficient to meet the criteria of hyperandrogenemia. As a general rule, a total

NICHD Reproductive Medicine Network
PPCOS-Pregnancy in Polycystic Ovary Syndrome Protocol

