3. Patients with hyperprolactinemia (defined as two prolactin levels at least one week apart > 30 ng/mL or as determined by local normative values). The goal of eliminating patients with documented hyperprolactinemia is to decrease the heterogeneity of the PCOS population. These patients may be candidates for ovulation induction with alternate regimens (dopamine agonists). A normal level within the year prior to date of consent is adequate for entry.
4. Patients with known 21-hydroxylase deficiency or other enzyme deficiency leading to the phenotype of congenital adrenal hyperplasia. 21-hydroxylase deficiency will be excluded in all patients by a fasting 17-hydroxyprogesterone (17-OHP) level < 2 ng/mL(24). If relevant, this level should be determined in the follicular phase (if the patient is in the luteal phase of an infrequent ovulatory cycle). In the case of elevated fasting 17-OHP levels, an ACTH stimulation test will be performed. A 1-hour stimulated value > 10 ng/mL will be an exclusion (24). As 21 hydroxylase

NICHD Reproductive Medicine Network
PPCOS-Pregnancy in Polycystic Ovary Syndrome Protocol
deficiency is a congenital condition, any normal level in the past of

17-hydroxyprogesterone allows entry into this study.

5. Patients with menopausal levels of FSH (> 20 mIU/mL). A normal level obtained within one year prior to date of consent is adequate for entry.
6. Patients with uncorrected thyroid disease (defined as TSH < 0.2 mIU/ML or >5.5 mIU/mL). A normal level obtained within the year prior to date of consent is adequate for entry.
7. Patients diagnosed with Type I or Type II diabetes (defined as a fasting serum glucose > 125 mg/dL on two occasions (25)), or patients receiving antidiabetic medications such as insulin, thiazolidinediones, acarbose, or sulfonylureas; patients currently receiving metformin XR for a diagnosis of Type I or Type II diabetes are also specifically excluded. A normal level within the year prior to date of consent is adequate for entry.
8. Patients with liver disease defined as AST or ALT > 2 times normal or total bilirubin >2.5 mg/dL. These labs must be drawn within 30 days prior to randomization.
9. Patients with renal disease defined as BUN > 30 mg/dL or serum creatinine > 1.4 mg/dL. These labs must be drawn within 30 days prior to randomization.
10. Patients with significant anemia (Hemoglobin < 10 mg/dL). This lab must be drawn within 30 days prior to randomization.

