All patients will fill out the American College of Obstetricians and Gynecologists risk factor questionnaire (See Appendix B for copy of the questionnaire) for genetic disease and if indicated, further counseling about genetic risks will be coordinated by the P.I. at each site. Patients who are rubella non-immune will be offered the rubella vaccine, and their entry into the study delayed for 1 month as per CDC recommendations. Patients who are HIV positive will receive appropriate counseling and will be advised about the need for medical treatment to prevent HIV transmission to their fetus during pregnancy. Thus, all patients who are rubella non-immune or are HIV positive will be eligible to participate in the study. The cost of rubella and HIV screening will be the responsibility of the patient. The site may cover this cost for patients without insurance benefits.

NICHD Reproductive Medicine Network
PPCOS-Pregnancy in Polycystic Ovary Syndrome Protocol
Progestin withdrawal

All patients, except those with evidence of a luteal phase progesterone level on baseline screening, will undergo withdrawal bleeding with progestin. The patient will be given a supply of progestin, for example medroxyprogesterone acetate 5mg x 10 days, and progestin therapy can be instituted immediately after the screening visit at the discretion of the P.I. The P.I. may elect to give another comparable form of oral progestin to institute a withdrawal bleed. Each site will provide this progestin and there will be no charge to the patient.

Screen failures

It is anticipated that patients who may fail screening due to a medically treatable condition, such as hypothyroidism, or mild iron deficiency anemia, may eventually become eligible for re-screening, assuming that other inclusion/ exclusion criteria have not changed (e.g. oligo-amenorrhea as an inclusion criteria, or elevated prolactin levels as an exclusion criteria). These cases will be handled on an individual basis after consultation with the DCC.

Counseling about timing of intercourse

All subjects will receive counseling about the need for regular intercourse during the study by the nurse coordinator at this visit. See guidelines below.

4. Timing of Intercourse Instructions

All subjects (and couples where the male partner is present) will be instructed to have intercourse 2-3 times per week. The optimal frequency will be every 2-3 days.

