Potential risks include those of obtaining the screening tests by venipuncture, and the use of medications. The risk of venipuncture includes discomfort and potential anemia. We are excluding patients at baseline with anemia and the amount of blood we are removing in our weekly tests (<10mL) is unlikely to cause anemia. Some women may additionally require a sonohysterogram or hysterosalpingogram and/or an ACTH stimulation test. There is a potential risk of an idiopathic reaction to Cortrosyn (cosyntropin) used in the ACTH stimulation test, but this is extremely rare (< 0.1%). The risks of an ACTH stimulation test are minimized by utilizing trained nursing personnel with investigator back up during the test. A hysterosalpingogram involves the risk of pain, bleeding, damage to uterus, pelvic infection, interrupting an unrecognized pregnancy, small amount of radiation exposure, and risk of an allergic reaction to the iodine containing radiocontrast. This test should not be performed with the patient on metformin XR therapy. A sonohysterogram involves the risk of pain, bleeding, damage to uterus, pelvic infection, and interrupting an unrecognized pregnancy. These tests are performed routinely as part of an infertility evaluation. It is not anticipated that a laparoscopy will be performed as part of this protocol.

NICHD Reproductive Medicine Network
PPCOS-Pregnancy in Polycystic Ovary Syndrome Protocol
Study women will be carefully screened for medical and reproductive

abnormalities prior to randomization. The risks of the medications will be lowered through nursing education and frequent follow-up. Study subjects will be monitored on at least a monthly basis for adverse reactions. Only a limited supply of medication will be dispensed at each visit to encourage compliance with the protocol and prevent a prolonged exposure of an early gestation to medication. All medication will be withheld for a week prior to exposure to iodine containing dyes. All records will be kept with strict confidentiality. No names will be used in the presentation of this data.

M. Study Monitoring

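### The anaemia exclusion is printed as haemoglobin below 10 mg/dL, a level no candidate can fall below, so read literally it excludes nobody and contradicts two later sections of the protocol

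*Protocol*

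**What the plan says.** The protocol deals with anaemia at entry in three places.

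- **Section IV.A.2, Exclusion Criteria, item 10**, sets the threshold: "Patients with significant anemia (Hemoglobin < 10 mg/dL". On timing it adds: "This lab must be drawn within 30 days prior to randomization".
- **Section IV.E.3, Screen failures**, gives examples of treatable reasons for failing screening, "such as hypothyroidism, or mild iron deficiency anemia, may eventually become eligible for re-screening".
- **Section IV.L, Other Risks of Procedures**, relies on the exclusion when it weighs the risk of weekly venipuncture: "We are excluding patients at baseline with anemia and the amount of blood we are removing in our weekly tests (<10mL) is unlikely" to cause anaemia.

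Item 10 is the only place where a haemoglobin threshold is given. The complete blood count appears in the Safety Screen column of Table 1 in section IV.E.3. That section also withholds from safety labs the general permission to accept results up to a year old.

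The opening of section IV.A.2 contains a general allowance: "Local laboratory cutoffs for inclusion/exclusion values may vary according to assay methodology". The item just before the anaemia criterion is stated in mg/dL: "Patients with renal disease defined as BUN > 30 mg/dL or serum creatinine > 1.4 mg/dL".

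**The concern.** The printed unit puts the threshold far below any haemoglobin value that a candidate could have. An eligibility rule that cannot be met has no effect, yet the protocol treats this one as working. It requires a fresh test for it, names anaemia as a cause of screen failure, and cites the exclusion in its account of procedural risk.

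At stake is whether the entry criteria can be applied as written. A criterion in the safety screen should not depend on 12 centres each noticing and correcting the unit for themselves. Until it is corrected, the text of item 10 does not support what sections IV.E.3 and IV.L say about it.

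**Working it through.** There is no statistical figure to reproduce here. The check is a unit conversion followed by a comparison of sections.

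**Inputs**
- Printed cutoff: haemoglobin < 10 mg/dL (section IV.A.2, item 10).
- Conversion: 1 g = 1,000 mg.
- Haemoglobin range in living adults: assumed to be about 3 to 18 g/dL. The documents give no range. This one is deliberately wide.

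**Step 1. Convert the printed cutoff.**
10 mg/dL ÷ 1,000 = 0.01 g/dL.

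**Step 2. Express the assumed range in the printed unit.**
3 g/dL × 1,000 = 3,000 mg/dL; 18 g/dL × 1,000 = 18,000 mg/dL.

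**Step 3. Compare.**
3,000 ÷ 10 = 300; 18,000 ÷ 10 = 1,800. The lowest value in the range is 300 times the cutoff and the highest is 1,800 times. The condition is false at every value, so the share of candidates excluded is 0%. This result does not depend on which unit was intended. Only the statement that the error is a factor of 1,000 assumes that g/dL was meant.

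**Step 4. Look for a correction elsewhere.**
No other section restates the haemoglobin threshold. The general allowance in IV.A.2 covers cutoffs that differ by assay method and says nothing about units. Item 10 also has no clause referring to local normative values, whereas the prolactin item (item 3) does.

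**Step 5. Set the sections side by side.**
- Item 10 against IV.E.3: women are expected to fail screening for anaemia, but under the printed threshold none can fail on item 10.
- Item 10 against IV.L: the risk argument has two supports, the exclusion of anaemic women and a draw of under 10 mL. As printed, the first is missing and the second remains.

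**Step 6. Look for a likely source.**
Items 7 (glucose), 8 (bilirubin) and 9 (BUN and creatinine) are all in mg/dL. A unit carried over into item 10 is the simplest explanation.

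**The case against.** The strongest reply is that this is a typing slip with an obvious intent. Item 10 speaks of significant anaemia, two other sections presuppose a working exclusion, and the test is a routine blood count that sites read from their own laboratory's report. They would probably apply the number in that laboratory's usual unit. This stands, and it limits the practical effect. It does not make the printed criterion correct.

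A reader might also infer larger consequences, which the documents do not support:

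- **That none of the 678 women could be excluded.** 678 is the number to be randomised. An exclusion acts on women screened, and that number is not given.
- **That the wrong unit is built into the case report form or the randomisation system.** Section IV.E.6 says only that the system asks the site for eligibility information. No specification is shown.
- **That the safety of all weekly draws rests on this criterion.** Thirty draws of under 10 mL come to under 300 mL, but IV.L relies on the small volume as well as the exclusion. The protocol also requires good general health at entry, a physical examination within 30 days before randomisation, at least monthly monitoring for adverse reactions, and a repeat blood count at study drug termination.
- **That the supplemental analysis excluding women later found ineligible cannot be derived.** That analysis (section V.A) is exploratory and covers ineligibility in general. It does not turn on one item.
- **That the misprint is what lets cutoffs differ between sites.** The protocol openly accepts variation that depends on the assay.

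One further point stands. Section IV.E.3 refers to mild iron deficiency anaemia, while item 10 excludes significant anaemia. Correcting the unit may not by itself bring those two descriptions into line.

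**Conclusion.** The point holds as an error in an operative eligibility criterion. As printed, the threshold is 0.01 g/dL, which is 300 to 1,800 times below the assumed adult range, so item 10 taken literally excludes no candidate. It is inconsistent with the screen-failure text in IV.E.3 and removes one of the two supports for the venipuncture argument in IV.L.

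The conclusion that nobody is excluded rests only on the wide assumed range. That the cause is a carried-over unit, and that sites would read past it, are judgements: likely, but not shown in the document. On those judgements the practical effect is probably small. The sample size, alpha level and primary comparison of live birth rates do not depend on this item.

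**What to change.** The sponsor should:

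1. Confirm the intended unit for haemoglobin in exclusion 10 and correct the text.
2. Reconcile item 10 with sections IV.E.3 (Screen failures) and IV.L, including the difference between mild and significant anaemia, so that all three describe the same exclusion.
3. Check that the confirmed unit is used wherever the criterion is applied, including any case report form or eligibility question that carries it.

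The cost is a small text correction and a document check, with no effect on design or analysis. The clinical cutoff is for the sponsor to confirm; none is proposed here.

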Ideally, the threshold for identifying a minimum difference between treatments is informed by prior data on a variety of factors important for decision making, including efficacy in randomized trials, effectiveness in clinical practice, side effects, patient values for benefits, side effects, and risks of each treatment, health-related quality of life, and costs. Unfortunately, data that would allow estimation of these factors for the clinical situation addressed by this protocol are unavailable.

In the absence of specific data, we assume that any combination of two or more drugs must be superior to either agent alone in order for the combination to be considered the "best" treatment. In other words, given that combination therapy inevitably will cost more than either agent alone, that it will carry the risks of the side effects of both agents, and be less convenient for patients than either alone, the combination of metformin plus clomiphene citrate must be superior to either agent alone by some amount in order for it to become the treatment of choice.

We propose that an absolute difference in live birth rates after 6 months of therapy of **15%** is clinically important.

3. Null Hypotheses

NICHD Reproductive Medicine Network
PPCOS-Pregnancy in Polycystic Ovary Syndrome Protocol

(A) The live birth rate after 30 weeks of therapy with the combination of metformin plus clomiphene citrate is not different from the live birth rate after either metformin alone or clomiphene alone.

(B) The live birth rate after 30 weeks of therapy with metformin alone is not different from the live birth rate after clomiphene alone.

4. Possible Study Outcomes and Interpretation:

a) Null hypothesis (A) is rejected

If the null hypothesis is rejected, we expect that combination therapy is superior to either agent alone, and, barring significant differences in adverse events, combination therapy becomes the treatment of choice.

b) Null hypothesis (A) is accepted, but null hypothesis (B) is rejected

If the difference between combination therapy and one of the single agents is less than 15%, then null hypothesis (A) is accepted. If the observed difference between the single agents is greater than 15%, we expect that metformin would become the treatment of choice, barring substantial differences in adverse events. (This also allows for the possibility that Metformin alone will be at least 15% more effective than clomiphene alone).

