c) The null hypothesis is accepted, but no statistically significant differences are observed between any of the treatments.

If the observed differences between all three agents are less than 15%, then the choice of initial treatment will likely be based on side effects, convenience, costs, etc.

Although this trial will not be able to definitively answer that issue, data collected from this study will allow planning of additional studies to address issues of cost-effectiveness, health-related quality of life, patient preferences, etc.

NICHD Reproductive Medicine Network
PPCOS-Pregnancy in Polycystic Ovary Syndrome Protocol
Given these considerations, at most two comparisons are needed

- Scenario 1: Point estimate of live birth rate with combination therapy higher than with either agent alone

Comparisons: (1) Combination therapy vs. highest single agent, (2) single agents to each other.

Rationale: In order to be preferred, combination therapy needs to be superior to both agents. If combination is not superior to the agent with the highest live birth rate, demonstration of superiority to the other agent is not clinically meaningful. Direct comparison of single agents becomes the critical comparison for decision making.

- Scenario 2: Combination therapy less effective than one of the single agents

Comparisons: 1

Rationale: Given cost, complexity, side effects, etc., combination therapy must be demonstrably more effective than single agent therapy in order to be clinically preferable. In this scenario, only the comparison between the two single agents is meaningful.

5. Sample Size Calculations

Primary Endpoint - Live Birth Rate

Assumptions

- 15% absolute difference considered to be clinically meaningful
- 15% dropout rate
- Overall alpha level = 0.05, two-tailed test
- Two planned comparisons

NICHD Reproductive Medicine Network
 PPCOS-Pregnancy in Polycystic Ovary Syndrome Protocol

1) Lowest rate vs. second lowest rate

2) Second lowest rate vs. highest rate

- χ^2 test for differences in proportions
- Best estimated live birth rates:
 - 1) Metformin alone: **30%**
 - 2) Clomiphene alone: **25%**
 - 3) Metformin + clomiphene citrate: **45%**

Parameters for sample size calculations:

- Alpha = **0.025**, two-tailed tests since two planned comparisons
- Beta = **0.20**, or 80% power

Sample Size

Treatment 1 (live birth rate)	Treatment 2 (live birth rate)	Required Sample Size	Sample Size with dropout adjustment	Total Sample Size

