The completed case report forms (CRF) will follow these guidelines: All data on the CRFs will be entered in ink. No data entry in the original CRF may be deleted or corrected by erasure, use of ink eradication fluid or any other such means. When a data entry is in error, draw a single line through the erroneous entry (the original data must remain discernible) and indicate the correct data in whatever way is appropriate. These changes should be initialed by the P.I. or designated study coordinator. Validity of data

NICHD Reproductive Medicine Network
PPCOS-Pregnancy in Polycystic Ovary Syndrome Protocol
recorded on CRFs during each patient visit will be attested to by one of the investigators
by a dated signature on an appropriate CRF page. All questions should be answered.
Data management will be as per DCC guidelines.

R. Competency to perform procedure/tests in the protocol

The principal investigator will be responsible for ensuring that laboratory and patient tests performed as part of the study are performed by competent personnel. These tests include semen analysis, ultrasonography of the pelvis, sonohysterography and/or hysterosalpingography of the uterus and fallopian tubes. The criteria for determination of competency may vary between sites in the study.

V. DATA ANALYSIS

All statistical tests will test non-directional hypotheses. The level of significance will be set at 0.05 for primary analyses and 0.05 for secondary analysis. An intent-to-treat principle will be employed during the primary analysis of the primary efficacy and safety measures. For the intent-to-treat analyses, randomized women will be included regardless of whether or not the patient received the assigned treatment, the patient was compliant with the treatment plan, and/or the treatment was administered according to randomization assignment.

A. Primary Efficacy Measure

Primary Analysis: A live birth will be defined as delivery of any viable infant. The primary analysis of the primary endpoint will include the following procedures. A chi-square test for equal proportions will be performed to evaluate whether live birth rate in Metformin/clomiphene group is the same as one in the group of either Metformin alone or clomiphene alone that has the higher live birth rate. If the test is not significant, a standard chi-square test will be used to examine differences in proportions in live births

NICHD Reproductive Medicine Network

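### IV.B.4 accepts the null hypotheses by a 15-point difference while V.A tests them by chi-square, and outcome (b) has no branch for clomiphene being ahead

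*Protocol*

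**What the plan says.** Protocol IV.B.3 states both nulls as zero difference. The second reads: "B) The live birth rate after 30 weeks of therapy with metformin alone is not different from the live birth rate after clomiphene alone".

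The synopsis and V.A decide them by chi-square: the combination against the better single agent and, if that is not significant, the single agents against each other. V.A: "A chi-square test for equal proportions will be performed to evaluate whether live birth rate in Metformin/clomiphene group is the same" as in that comparator. V.A sets the level at 0.05; the sample size section, IV.B.5, uses 0.025 per comparison.

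IV.B.4, on possible outcomes and their interpretation, uses a different criterion:
- Outcome (b), null (A): "If the difference between combination therapy and one of the single agents is less than 15%, then null hypothesis (A) is accepted".
- Outcome (b), single agents: "If the observed difference between the single agents is greater than 15%, we expect that metformin would become the treatment of choice", followed by the parenthesis "This also allows for the possibility that Metformin alone will be at least 15% more effective than clomiphene alone".
- Outcome (c) is headed "The null hypothesis is accepted, but no statistically significant differences are observed between any of the treatments", but its text begins "If the observed differences between all three agents are less than 15" percent.

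Outcome (a), rejection of (A), carries no 15-point condition.

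**The concern.** The 15 points enter the plan as the clinically important difference (IV.B.2) and as the true difference used for sizing (IV.B.5). In IV.B.4 they become a cut-off for accepting a null of zero difference. The sentence on null (A) does not say *observed*, but the next sentence and outcome (c) do, and a null can only be decided from trial data by what is observed. Outcome (c) treats non-significance and an observed difference below 15 points as the same thing, which they are not.

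The same data could thus be reported as rejecting (A) under V.A and as accepting it under IV.B.4. In outcome (b) the condition on the single agents has no direction but the consequence always names metformin. A clomiphene lead of more than 15 points has no branch that fits it.

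**Working it through.** **Inputs (IV.B.5, IV.C.2, V.A).** Rates 45% combination, 30% metformin, 25% clomiphene; 226 per arm (197 before the dropout adjustment); two-sided tests; no continuity correction; alpha 0.025 (IV.B.5) or 0.05 (V.A). Both alphas are carried through.

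**1. The plan's own figure.** Pooled-variance formula, 45% v 30%, alpha 0.025, 80% power:

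n = [2.2414·√(2·0.375·0.625) + 0.8416·√(0.45·0.55 + 0.30·0.70)]² / 0.15² = (1.5346 + 0.5693)² / 0.0225 = 196.7, so 197.

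This matches the table, as do the other rows (206, 185, 168). The trial is sized for the chi-square test to detect a true 15 points, not for the observed difference to reach 15.

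**2. Smallest significant difference at 226 per arm.** z = (x₁ − x₀)/226 ÷ √[p̄(1 − p̄)·2/226], with x₀ = 68 births (30.1%):

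| Births | Difference (points) | z | Result |
|---|---|---|---|
| 88 v 68 | 8.8 | 1.98 | significant at 0.05 (limit 1.96) |
| 91 v 68 | 10.2 | 2.27 | significant at 0.025 (limit 2.24) |

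An observed 45% v 30% gives z = 0.15/√(0.375·0.625·2/226) = 3.29, p = 0.001. The rules therefore conflict from 8.8 or 10.2 points up to 15.

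A result inside that range: 95 v 68 births is 27/226 = 11.9 points. Here p̄ = 163/452 = 0.3606, so z = 0.1195/0.0452 = 2.64, significant at either alpha. The 95% interval is 0.1195 ± 1.96·√[(0.4204·0.5796 + 0.3009·0.6991)/226] = 0.1195 ± 0.0879, or 3.2 to 20.7 points. V.A rejects (A); IV.B.4 accepts it; the interval includes 15.

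**3. How often the rules conflict.** Simulation of three arms at 45/30/25%, 226 each, combination against the higher single agent, 2,000,000 replicates:

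| Event | alpha 0.05 | alpha 0.025 |
|---|---|---|
| Chi-square rejects, combination better | 90.8% | 85.1% |
| Observed difference at least 15 points | 49.8% | 49.8% |
| Rejects, but below 15 points | 41.0% | 85.1 − 49.8 = 35.3% |

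The subtraction in the last cell is valid because at these rates a difference of 15 points is well beyond the significance limit. Against the 30% arm alone, the exact probability of observing at least 15 points is 51.7%.

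**4. Direction in outcome (b).** Suppose clomiphene has 102 births and metformin 68: 34/226 = 15.04 points, z = 3.30. V.A would show clomiphene significantly better. The condition in (b) is met, and its text still names metformin.

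**The case against.** The decision procedure itself is stated consistently. The synopsis, V.A and the sample size assumptions all specify chi-square, and V.F leaves the critical value to the detailed analysis plan. IV.B.4 sits inside the sample size section, gives no test and no alpha, and uses soft verbs in places. Its 15 points can be read as loose shorthand for the difference the trial was sized to detect. Weighing the estimate against a clinically important difference is also sound, since IV.B.2 explains why the combination must be better by some amount.

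Much of this stands, and it rules out three stronger readings that a reader might infer:

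- *The plan cuts power to about 50%.* It does not. By chi-square the power is 85-91%. An approximately unbiased estimate exceeds its true value about half the time in any trial, so the 50% shows only that the design difference makes a poor cut-off.
- *The analysis would declare metformin the winner even if clomiphene led.* Nothing in V.A does so. The sentence is an expectation, written with metformin planned at 30% and clomiphene at 25%. At those rates a single-agent difference above 15 points has a probability of about 0.9%. The gap matters if the rates depart from plan.
- *Accepted means shown to be equal.* Outcome (c) makes no equivalence claim. It leaves the choice to side effects, convenience and cost, so the term is mainly a matter of terminology.

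The objection does not remove the contradiction. The sentence on null (A) is an unhedged accept rule for a zero-difference null, and the protocol does not say that V.A overrides it.

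**Conclusion.** The point holds as a contradiction between sections, not as a defect in the primary test. IV.B.4(b)-(c) and V.A give opposite answers on null (A) for observed differences from about 9 points (alpha 0.05) or 10 points (alpha 0.025) up to 15. At the planning rates that is about 41% or 35% of trials. The fall to about 50% would apply only if IV.B.4 were used to decide the hypothesis. Outcome (b) separately lacks a branch for clomiphene being ahead.

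The figures assume 226 women analysed per arm, the planning rates at face value, an uncorrected chi-square and no allowance for the interim look. Which of the two stated alphas applies is a separate question; the conclusion is the same under either. The severity is that of a wording reconciliation, to be made before unblinding.

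**What to change.** Reconcile IV.B.4 with V.A:

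1. State that the V.A chi-square result at the allocated alpha, with its direction, decides (A) and (B), and remove the 15-point condition from the acceptance of (A).
2. Keep 15 points as a separate clinical-importance benchmark. Report each difference in live birth rate with its confidence interval and read the interval against 15.
3. In (b), replace metformin by *the single agent with the significantly higher live birth rate*.
4. In (c), use one criterion, non-significance, in both the heading and the text. Writing *not rejected* for *accepted* is a tidy optional change.

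The cost is protocol wording and a few reported intervals. The test, sample size and data collection stay as they are.
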